9.5.2 Medication Errors

Any medication error that results in an AE, even if it does not meet the definition of serious, requires reporting within 24 hours to the safety monitor.

9.6 STUDY STOPPING RULES

9.6.1 Stopping Rules for Study

Kadmon reserves the right to discontinue the trial at any time for the following reasons:

- 1. Failure to meet expected enrollment goals
- 2. Emergence of any safety information that could significantly affect continuation of the trial
- 3. Violation of GCP (R2), the Clinical Trial Program, or the contract by a trial site or Investigator, or any other administrative reasons, disturbing the appropriate conduct of the trial
- 4. Results from other competing clinical trials make this trial not worthy to continue

9.6.2 Stopping Criteria for Subjects

Subjects will be discontinued from the study at any time for the following reasons:

- 1. Grade \geq 3 LFT increase (AST, ALT, or total bilirubin)
- 2. Grade \geq 3 clinically significant toxicity considered related to belumosudil

3. QTc > 500 ms or AE of *Torsade de Pointe*

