3.9 TREATMENT DISCONTINUATION

Treatment discontinuation reasons include the following:

- An AE requiring permanent discontinuation of study drug
- Investigator decision
- Clinically significant disease progression. For example:
 - o mRSS increase ≥ 5 units
 - Absolute decrease in FVC (% predicted) ≥10% or absolute decrease in diffuse capacity of the lungs for carbon monoxide (DLco) (corrected for Hb) of > 15%
 - o Renal crisis
- Study stopping rules for the sponsor (Section 9.6.1)
- Subjects meeting criteria for discontinuation from the study (Section 9.6.2)

- Voluntary withdrawal by subject
- Noncompliance to protocol
- Subject lost to follow-up
- Termination of the study by sponsor
- Subject death

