4.5 TREATMENT COMPLIANCE

Subjects will be given a study drug diary to record the details of each dose of study drug. Diaries will be dispensed/collected on each visit. Compliance with oral dosing will be confirmed using patient diaries, which will be examined at each visit by site staff to determine if dosing is as instructed per protocol and follow-up with the subject accordingly. If the subject skips more than 7 consecutive days of drug dosing (other than those specified in the Dose Modification Guideline for Toxicity), the subject should be discontinued from the study unless approved by the Medical Monitor and Investigator.

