4.12 DOSE MODIFICATION GUIDELINES

Any clinically significant toxicity will necessitate consideration of either a pause or cessation of therapy. Dose modification of therapy is permitted in the open label phase as outlined in Table 5.Guidelines for management of treatment-emergent toxicities in subjects receiving belumosudil are outlined in Table 3Error! Reference source not found..

Table 3 Guidelines for Management of Treatment-emergent Toxicities (Double-blinded Phase)

Toxicity	Recommended Action
Grade \geq 3 LFTs (AST,	Complete the "Treatment-emergent LFT elevations" eCRF
ALT or total bilirubin)	Discontinue belumosudil
Other Grade ≥ 3	Discontinue belumosudil
clinically significant	
toxicities considered	
related to belumosudil	
Grade 2 clinically	Consider pause or cessation of therapy
significant toxicities	Dose interruption for toxicity will be permitted up to 14 days.
	• If toxicity does not resolve to Grade 1 or below for 14 days, subjects
	will be discontinued from treatment

ALT = alanine aminotransaminase; AST = aspartate aminotransaminase; eCRF = electronic case report form; LFT = liver function tests

Table 4 Guidelines for Management of Treatment-emergent Toxicities (Open-Label Phase)

(Open-Laber I hase)	
Toxicity	Recommended Action
Grade ≥ 3 LFTs (AST, ALT or total bilirubin)	Complete the "Treatment-emergent LFT elevations" eCRF Discontinue belumosudil
Other Grade ≥ 3 clinically significant toxicities considered related to belumosudil	Discontinue belumosudil
Grade 2 clinically significant toxicities	 Consider pause or dose modification(table 5) of therapy Dose interruption for toxicity will be permitted up to 14 days. If toxicity resolves to grade 1 or below then consider resuming belumosudil at current dose or one dose decrement as outlined in Table 5 below If toxicity recurs, hold dose as above then consider resuming belumosudil at one dose decrement If toxicity does not resolve to Grade 1 or below for 14 days, subjects will be discontinued from treatment

ALT = alanine aminotransaminase; AST = aspartate aminotransaminase; eCRF = electronic case report form; LFT = liver function tests

Dose interruption for toxicity management for 14 days is permitted. Subjects requiring pauses of more than 14 days will be discontinued from the study unless approved by the Medical Monitor.

Table 5. Belumosudil Dose Decrements

Belumosudil Dose	Dose Reduction
200 mg BID	200 mg QD
200 mg QD	200 mg QOD

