- Patient Global Assessment
- PFTs (\pm 7 days)
- HRCT (\pm 7 days)
- Skin biopsies (optional)
- Sampling for PD
- Complete PE
- Vital signs
- Weight
- Hematology and chemistry
- Urinalysis
- 12-lead ECG
- Pregnancy test
- Collect study diary
- Collect study drug
- Concomitant medication assessment
- AE assessment

Kadmon Corporation, LLC

Subjects who discontinue from the study prior to Week 52 will have the same assessments performed as subjects who complete Week 52.

5.5 28-DAY FOLLOW-UP VISIT

Subjects will return to the clinic twenty-eight (28) days (\pm 3 days) after their last dose of study drug. At this visit, the following procedures will be completed:

- CRISS
- mRSS
- SHAQ-DI
- Physician Global Assessment
- Patient Global Assessment
- PFT
- Complete PE
- Vital signs
- Weight
- Hematology and chemistry
- Urinalysis
- 12-lead ECG
- Pregnancy test
- Concomitant medication assessment
- AE assessment

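### Protocol 4.12 and 9.6.2 send the same events to different exits (off drug, or out of the study), and nothing secures a Week 24 measurement once drug is stopped

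*Protocol*

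**What the plan says.** **Same event, two outcomes**

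| Event | Protocol 4.12, Tables 3 and 4 | Elsewhere |
|---|---|---|
| Grade 3 or higher AST, ALT or total bilirubin | "Discontinue belumosudil" | 9.6.2: "Subjects will be discontinued from the study at any time for the following reasons" |
| Related, clinically significant Grade 3 or higher toxicity | "Discontinue belumosudil" | 9.6.2: same sentence |
| Toxicity outlasting a 14-day interruption | "If toxicity does not resolve to Grade 1 or below for 14 days, subjects will be discontinued from treatment" | Text under the tables: "Subjects requiring pauses of more than 14 days will be discontinued from the study unless approved by the Medical Monitor" |

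Protocol 3.9, which lists reasons for stopping treatment, includes meeting the 9.6.2 study-exit criteria as one of them. SAP 3.3 counts stopping treatment and leaving the study as two separate dispositions.

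**A separate route out.** Protocol 4.5 covers more than 7 consecutive skipped days: "the subject should be discontinued from the study unless approved by the Medical Monitor and Investigator". It excludes interruptions made under the toxicity guideline.

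**What is measured afterwards.** Protocol 3.7 asks that subjects who withdraw attend End-of-Treatment and 28-day visits. Protocol 5.4 adds: "Subjects who discontinue from the study prior to Week 52 will have the same assessments performed as subjects who complete Week 52". Appendix A defines End of Treatment as early withdrawal or Week 52. Protocol 5.2 says in general terms that enrolled subjects undergo all later evaluations, without mentioning subjects off drug.

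**How the analysis treats it.** The primary endpoint is CRISS at Week 24 in all dosed subjects. Under SAP 3.1.7.1, once a subject stops study drug for any reason, the last value before stopping is carried forward, and randomized patients with no post-baseline observation are left out. For mRSS, FVC, the two global assessments and SHAQ-DI, SAP 3.8.2.1 to 3.8.2.5 do not impute.

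**The concern.** Stopping drug and leaving the study are different things in an analysis of everyone dosed. The first is an event during treatment, after which the Week 24 outcome can still be measured. The second ends measurement. Where the protocol gives both for one event, two sites can handle the same subject differently and both be compliant, and the two disposition counts in SAP 3.3 lose their meaning.

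At stake is the observed Week 24 value. Appendix A schedules the CRISS components in the blinded period only at Weeks 8, 16, 24 and 28, so each lost visit counts. A carried-forward score describes an earlier time. CRISS Step 1 also sets the score to 0.0 for certain organ events during the trial (SAP 3.8.1), whereas routine adverse event collection ends 28 days after the last dose (Protocol 9.1). An unrelated Step 1 event after that, but before Week 24, might not be recorded in a subject who has left.

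**Working it through.** **1. The plan's own figure.** The only calculation tied to the sample size is the chance of seeing at least one adverse event among 20 subjects (Protocol 9.9), 1 − (1 − p)^20:
- p = 0.14: 1 − 0.86^20 = 0.951, stated as above 90%
- p = 0.10: 1 − 0.90^20 = 0.878, stated as above 80%

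Both reproduce. No dropout rate enters, and Protocol 9.7.2 says the size is not driven by hypothesis testing. The documents therefore give no planned loss to compare with.

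**2. Following one subject through the text.** Suppose related Grade 3 toxicity occurs at Week 10.
- Under 9.6.2 the subject leaves the study: an End-of-Treatment visit at about Week 10 and a 28-day visit at about Week 14 (10 + 4), with no Week 16 or Week 24 visit.
- Under the 4.12 tables the subject stops drug. Study status is not stated, and only the general sentence in 5.2 points to continued visits.
- Under either reading, SAP 3.1.7.1 takes literally only values from before drug was stopped. Week 24 CRISS is then the Week 8 score, even if a Week 24 value was measured off drug.
- If drug had stopped before Week 8, there might be no usable post-baseline score at all, and the subject could drop out of the CRISS evaluation.

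**3. Illustrative size.** Let d be the proportion stopping before Week 24 with no Week 24 measurement (assumed). Two values of d are borrowed from the psoriasis study in Protocol 1.4.1.3: related Grade 3 or higher events (5/92 = 5.4%) and events leading to discontinuation (15/92 = 16.3%). Missing per arm is 20d. The standard error of an observed-only Week 24 difference grows by √(1/(1 − d)). Power for an assumed 0.8 SD difference, two-sided 5%, is Φ(0.8√(n/2) − 1.96) with n = 20(1 − d).

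| d | Missing of 20 | SE factor | Power |
|---|---|---|---|
| 0 | 0 | 1.000 | 0.72 |
| 5.4% | 1.1 | 1.028 | 0.69 |
| 10% | 2.0 | 1.054 | 0.67 |
| 16.3% | 3.3 | 1.093 | 0.64 |
| 30% | 6.0 | 1.195 | 0.56 |

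The chance that at least one of 20 is affected is 1 − (1 − 0.054)^20 = 0.67 at the low proxy and 1 − (1 − 0.163)^20 = 0.97 at the higher one. The last two columns apply to an analysis of observed Week 24 values only, such as the ANCOVA on the unimputed secondary endpoints. The repeated-measures model would recover part of the loss from earlier visits. For CRISS the count is kept by imputation, and the cost is a score from the wrong time.

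**4. Does stopping for progression distort CRISS?** Protocol 3.9 gives an mRSS rise of at least 5 and a fall in FVC% of at least 10 as examples of reasons to stop treatment. In the SAP 3.8.1 equation, with the other components unchanged (assumed):
- mRSS +5: exponent −5.54 − 0.81 × 5 = −9.59, score about 0.0001
- FVC% −10: exponent −5.54 − 0.21 × 10 = −7.64, score about 0.0005

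If that reading is the last one before drug is stopped, the value carried forward is already near zero.

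**The case against.** The best defence is that measurement does not end at drug stop. Early leavers get the Week 52 assessment set and a 28-day visit, both with the CRISS components. Protocol 5.2 has a general duty to complete evaluations, and the 14-day rule in the text allows Medical Monitor approval. The study is exploratory. All of this is correct, and it narrows the point to the Day 169 value. It does not remove the conflict between 4.12 and 9.6.2, and a general sentence cannot keep on schedule a subject whom another section takes off the study.

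A reader might infer more than the documents support:
- **That the treatment comparison is biased in a known direction.** In the psoriasis study, events leading to discontinuation were 16.3% on belumosudil and 16.7% on placebo. These near-equal rates show no imbalance, and they come from another disease, a longer treatment period and doses up to 600 mg/day.
- **That stopping for progression corrupts the primary score.** By step 4, such subjects would mostly carry forward a CRISS near zero. Renal crisis and worsening lung fibrosis are set to 0.0 in Step 1.
- **That Protocol 4.5 contradicts 4.12.** It excludes toxicity interruptions and so concerns a different event.
- **That all the loss is avoidable.** In the psoriasis study, 40.9% ended early by subject withdrawal and 12.7% by loss to follow-up, against 5.5% for liver enzymes. Continued visits cannot recover withdrawn consent or lost contact.
- **That protocol wording alone would repair the primary analysis.** SAP 3.1.7.1 as written would still pass over off-drug Week 24 values.

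**Conclusion.** The point stands in a limited form. Protocol 4.12 and 9.6.2 conflict over Grade 3 or higher liver tests and related Grade 3 or higher toxicity. Section 4.12 also conflicts with itself over toxicity outlasting 14 days, and 3.9 mixes the two statuses. For a subject taken off study before Week 24, the observed Week 24 value is lost. CRISS is then filled from before drug was stopped, and the secondary endpoints are left missing.

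The size rests on assumption: 5% to 30% stopping gives about 1 to 6 of 20 per arm, an upper bound on what could be recovered. Neither the size nor the direction of any bias can be derived from the documents. This should be corrected because the remedy is cheap, but it does not by itself invalidate the primary analysis. No view is taken on which stopping rule is clinically right.

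**What to change.** 1. Reconcile Protocol 3.9, 4.5, 4.12 and 9.6.2 so that stopping study drug and leaving the study are separate, defined statuses, without changing who stops drug or when. Use the same two terms as SAP 3.3.
2. State that subjects off drug who have not withdrawn consent keep the scheduled efficacy assessments through Week 24: mRSS, FVC, SHAQ-DI, physician and patient global assessments, and ascertainment of the CRISS Step 1 events.
3. Amend SAP 3.1.7.1, and the matching imputation text in 3.8.1, so that an observed Week 24 value after drug discontinuation is used for CRISS. Keep carry-forward for values that are truly missing, or as a sensitivity analysis.

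The cost is protocol wording, a small SAP change and a few already-scheduled visits for subjects off drug. Off-drug values may dilute a drug effect. A sponsor who wants the on-drug picture can still obtain it from the carry-forward sensitivity analysis, whereas a Week 24 value never measured cannot be recovered.

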9.7 STATISTICAL CONSIDERATIONS

9.7.1 Hypothesis

This study will explore the efficacy of belumosudil (200 mg QD, 200 mg BID) compared to placebo on proposed primary, secondary, and exploratory endpoints. The main focus is to provide guidance for the follow up studies.

9.7.2 Sample Size

This is an exploratory study; sample size and power are not driven by hypothesis testing. A total of 60 subjects will be randomized (1:1:1) to receive orally administered belumosudil 200 mg QD (n = 20), belumosudil 200 mg BID (n = 20), or matched placebo (n = 20).

9.7.3 Analysis Populations

Two populations will be employed in the analysis of study data:

- The mITT Population will consist of all subjects who receive at least 1 dose of study drug.
- The Evaluable for Efficacy/Activity Population will consist of subjects who have received at least 80% of expected study drug and have post-baseline efficacy data.

The primary analysis will be performed on the mITT Population.

9.7.4 Data Analysis

All pre-specified analyses will be described in a Statistical Analysis Plan (SAP).

Demographics, subject disposition, and screening and baseline characteristics will be summarized in each population and by group.

9.7.5 Interim Analysis

Kadmon Corporation, LLC

There is no interim analysis planned.

9.8 **EFFICACY ANALYSIS**

9.8.1 Primary Efficacy Endpoint

The primary efficacy endpoint of this study is to evaluate the efficacy of belumosudil compared to placebo for the CRISS score at Week 24

9.8.2 Secondary Efficacy Endpoints

Secondary endpoints are as follows:

- To assess the CRISS for each group at Week 52
- To evaluate the efficacy of belumosudil compared to placebo at Week 24 for:
 - o mRSS
 - o FVC
 - o Physician global assessment
 - Patient global assessment
 - SHAQ-DI
- To evaluate the efficacy of belumosudil at Week 52 compared to baseline for subjects randomized to belumosudil for the parameters in the bullet above
- To assess changes in lung fibrosis via HRCT performed at baseline, Weeks 24, and Week 52 only in subjects with ILD at screening
- To assess the PK of belumosudil by sparse sampling of belumosudil on Weeks 4 and 8 (i.e., Days 29 and 57) immediately prior to belumosudil dosing and 3 hours post-dose
- To assess the safety of belumosudil compared to placebo in subjects with dcSSc by examining the percentage of subjects with TEAEs by CTCAE v5.0 in subjects with diffuse cutaneous systemic sclerosis

9.8.3 **Exploratory Efficacy Endpoints**

Exploratory endpoints are as follows:

Kadmon Corporation, LLC

- To evaluate changes in biomarkers of endothelial cell dysfunction, fibrosis, immune system function, and cytokine alterations from subjects receiving belumosudil or placebo
- To assess histology and gene expression from skin biopsies taken from subjects at baseline, Week 24, and optionally at Week 52

9.8.4 Analysis Method

- Mixed models with treatment and week as fixed effects, and subject as random effect will be used to analyze all longitudinal efficacy endpoints.
- Descriptive statistics will be provided for all endpoints by treatment groups and visits.

9.9 SAFETY ANALYSES

Treatment exposure will be summarized.

The TEAEs will be evaluated using the CTCAE v5.0. The total sample size of 20 subjects per belumosudil dose group will provide > 90% probability of one or more belumosudil subjects experiencing an AE that has an underlying rate of \geq 14% and > 80% probability of one or more subjects in the study experiencing an AE that has an underlying rate of \geq 10%.

The TEAEs will be summarized overall and by group using Medical Dictionary of Regulatory Activities Version 21.0 (MedDRA v21.0) or higher, System Organ Class (SOC) and preferred term (PT), classified from verbatim terms. The incidence and percentage of subjects with at least one occurrence of a preferred term will be included, according to the most severe grade using a 5-point scale (mild, moderate, severe, life threatening, or death). The number of events per preferred term will also be summarized. Causality (relationship to study treatment) will be summarized separately.

AEs, SAEs, related AEs, related SAEs, Grade ≥ 3 AEs, related Grade ≥ 3 AEs, and AEs leading to withdrawal or treatment discontinuation will be summarized overall and by group according to SOC and PT. Adverse events will also be presented in listings. Duration of AEs will be determined and included in listings, along with action taken and outcome.

Laboratory results will be graded; Incidence of laboratory abnormalities will be summarized. The worst on-study grade after the first dose of study drug will be summarized. The incidence of Grade ≥ 3 laboratory abnormalities under treatment and shifts in toxicity grading from baseline to highest-grade post-baseline will be displayed.

Vital sign measurements and ECGs will be summarized by group at each scheduled time point using descriptive statistics and included in data listings.

Page 70 of 99

9.10 PHARMACOKINETIC ANALYSES

Further details will be described in the SAP.

9.11 DATA QUALITY ASSURANCE

Accurate and reliable data collection will be ensured by verification and cross check of the eCRFs against the Investigator's records by the study monitor (source document verification) and by the maintenance of a drug—dispensing log by the Investigator. Collected data will be entered into a computer database and subject to electronic and manual quality assurance procedures.

Kadmon Corporation, LLC

10. REGULATORY OBLIGATIONS

This study will be conducted in compliance with GCP, including International Conference on Harmonization of Technical Requirements for Registration of Pharmaceuticals for Human Use, and in general, consistent with the most recent version of the Declaration of Helsinki. In addition, the Investigator agrees to adhere to all applicable local laws and regulatory requirements relevant to the use of new therapeutic agents in the countries involved.

The study is to be conducted in compliance with the protocol. The appropriate IRBs/IECs must approve the protocol and any amendments, and the subject ICF before implementation.

Freely given written informed consent must be obtained from every subject before participation in this clinical trial. The rights, safety, and well-being of participating subjects are the most important considerations and should prevail over interests of science and society.

Study personnel involved in conducting this trial will be qualified by education, training, and experience to perform their respective task(s). This trial will not use the services of study personnel where sanctions have been invoked or where there has been scientific misconduct of fraud (e.g., loss of medical licensure, debarment).

27 May 2021

11. ETHICAL ASPECTS

11.1 LOCAL REGULATIONS

The study must fully adhere to the principles outlined in Guideline for Good Clinical Practice ICH E6(R2) Integrated Addendum to ICH E6(R1) (March 2018), and in general, be conducted in a manner consistent with the most recent version of the Declaration of Helsinki. The Investigator will ensure that the conduct of the study complies with the basic principles of GCP as outlined in the current version of 21 CFR, subpart D, Part 312, "Responsibilities of Sponsors and Investigators", Part 50, "Protection of Human Subjects", and Part 56, "Institutional Review Boards".

11.2 Informed Consent

Sample ICFs will be supplied to each site. Kadmon Corporation or its designee must review any ICF prior to submission for review by the IRB/IEC. The final IRB/IEC-approved document must be provided to Kadmon Corporation for regulatory purposes.

It is the responsibility of the Investigator, or a person designated by the Investigator, to obtain written informed consent from each subject (or the subject's legally authorized representative) participating in this study after adequate explanation of the aims, methods, anticipated benefits, and potential hazards of the study in accordance with federal and state regulations. In the case where the subject is unable to read, an impartial witness should be present during the entire informed consent discussion. After the subject has orally consented to participation in the trial, the witness' signature on the form will attest that the information in the consent form was accurately explained and understood. A copy of the ICF must be provided to the subject. If applicable, it will be provided in a certified translation of the local language.

The eCRF for this study contains a section for documenting informed subject consent, and this must be completed appropriately. Signed ICFs must remain in each subject's study file and must be available for verification by study monitors at any time. If new safety information results in changes in the risk/benefit assessment, the consent form should be reviewed and updated as necessary. All subjects (including those already being treated) should be informed of the new information, should be given a copy of the revised form, and should give their consent to continue in the study.

